## Randomized prospective study of particulate corticosteroid versus non-particulate corticosteroid for sacroiliac joint injection

### **Background and Significance**

In spinal Intervention dexamethasone has been found to be non-inferior to particulate corticosteroids such as methylprednisolone. Despite this, there is a theoretical benefit of particulate steroids as they are assumed to remain in the site of injection for a longer duration. Whether or not such difference in effectiveness has not been studied in intra-articular injections. In spine injections specifically, this has not been evaluated in the sacroiliac joint steroid injections.

Sacroiliac joint injections are frequently employed as a treatment for suspected sacroiliac joint pain. Success rates for these injections range widely, from 18% to 62% (1). Nearly all outcomes studies of sacroiliac joint corticosteroid injection utilize preparations of particulate corticosteroid. No reports of neurologic infarction or other catastrophic complications have been reported following sacroiliac joint injection with any form of steroid.

According to current Spine Intervention Society Guidelines, sacroiliac joints should be done with the use of image guidance including contrast administration with real-time fluoroscopy. If vascular uptake is appreciated during this, it is recommended the needle be repositioned. Vascular uptake is relatively frequent, with reports of an incidence of 5.3% (2) There are occasions wherein despite multiple attempts at needle repositioning, vascular uptake persists. In such cases, there is at least theoretical increased risk in administering particulate steroid and because of this the procedure may be cancelled. An alternative to avoid this risk/complication or procedure termination would be administration of a non-particulate steroid. However, no evidence exists to support the practitioner in determining if injection of the non-particulate corticosteroid dexamethasone has equal effectiveness compared to particulate preparations of corticosteroid.

### **Hypothesis**

Null Hypothesis: There is no difference in percentage of patients with sacroiliac joint pain as confirmed by positive anesthetic response (80% relief immediately after injection) to sacroiliac joint steroid injection that achieve moderate or good response (at least 50% improvement in numeric pain rating scale) between those receiving sacroiliac joint corticosteroid injection of 40mg of methylprednisolone and those receiving 10mg of dexamethasone at 4 weeks and 3 months.

### **Specific Aims:**

1. Compare the proportion of patients between groups with a good response (80% or greater improvement in index pain) after sacroiliac joint corticosteroid injection at 2-4 weeks and 3 months.

2. Compare the proportion of patients between groups with a moderate response (50% or greater improvement in index pain) after sacroiliac joint corticosteroid injection at 2-4 weeks and 3 months.
3. Compare the proportion of patients between groups who have at least 30% improvement in ODI at 2-4 weeks and 3 months
4. Compare the proportion of patients between groups who have ODI score less than 20% at 2-4 weeks and 3 months.
5. Compare the proportion of patients between groups who had a good response at 2-4 weeks that continue to have good response at 3 months
6. Compare the proportion of patients between groups who had a good response at 2-4 weeks that continue to have at least moderate response at 3 months.
7. Compare the number of patients who have at least moderate response at 2-4 weeks who require repeat injection prior to 3 months.
8. Compare the number of patients with cessation of pain medication use, other than over-the-counter medication, for index pain at 2-4 weeks and 3 months
9. Report Adverse Events

#### Recruitment Process

Identification of potential study participants on day they arrive to outpatient surgery center based on the treatment room's schedule.

#### Enrollment Process

Potential candidates will be approached on the day of their scheduled sacroiliac joint steroid injection with a presentation by a physician or research assistant. Eligibility will be determined by interview by physician or research assistant based on inclusion and exclusion criteria. Informed consent of qualifying volunteers will be obtained verbally and in written form.

#### Inclusion Criteria:

- aged >18, capable of understanding and providing consent in English, capable of complying with the outcome instruments used, capable of attending all planned follow up visits
- unilateral low back/buttocks pain of at least 2 weeks.
- Patient reported 7 day average of numeric pain rating score (NPRS) low back/buttocks pain of at least 5/10 at baseline evaluation
- Clinical diagnosis of sacroiliac joint pain as diagnosed by a board certified Physiatrist including history of low back/buttocks pain and at least 2 positive physical exam findings (including positive fortin finger sign, pain with palpation of posterior superior iliac spine, positive FABER's test, positive Gaenslan's test, positive sacral distraction, positive thigh thrust, positive lateral compression, positive sacral thrust)
- Patient consents to sacroiliac joint corticosteroid injection in a shared decision-making process with the treating physician.

- 80% or more relief of index pain within first 5-15 minutes after injection

#### Exclusion Criteria:

- Clinical suspicion of alternative process is greater than clinical suspicion of sacroiliac joint pain
- Those receiving remuneration for their pain treatment (e.g., disability, worker's compensation).
- Those involved in active litigation relevant to their pain.
- Those unable to read English and complete the assessment instruments.
- Those unable to attend follow up appointments
- The patient is incarcerated.
- History of prior sacroiliac joint fusion
- Progressive lower extremity neurologic deficit (from active radiculopathy, unhealed radiculopathy, or neuromuscular disease)
- Sacroiliac joint steroid injection within the prior 12 months
- 2 Positive lumbar medial branch blocks within the past 12 months
- Radiofrequency ablation of the lumbar spine within the past 12 months
- Lumbar facet steroid injections within the past 12 months
- Prior epidural steroid injection within the prior 3 months in any location within the spine.
- Possible pregnancy or other reason that precludes the use of fluoroscopy.
- Allergy to steroid, contrast media, or local anesthetics.
- BMI>40.
- Systemic inflammatory arthritis (e.g., rheumatoid arthritis, ankylosing spondylitis, lupus).
- Active infection or treatment of infection with antibiotics within the past 7 days.
- Medical conditions causing significant functional disability (e.g., stroke, decompensated COPD, decompensated heart failure)
- Chronic widespread pain or somatoform disorder (e.g. fibromyalgia).
- Addictive behavior, severe clinical depression, or psychotic features.

#### Outcome Instruments

*(The baseline examination and all baseline questionnaires will be completed within 2 weeks before the first injection).*

- Location of pain
- Duration of pain
- Demographics
- BMI

Baseline

Follow-up

- Adverse effects

-

Baseline and Follow-up

- NPRS back/buttocks pain (7-day average)
- Oswestry Disability Index (ODI)

Injection Treatment

Based on clinical evaluation patients will be scheduled for a unilateral fluoroscopic guided sacroiliac joint steroid injection. On arrival to the procedure center eligible patients will be enrolled and consented. Patients will then be randomized to receiving sacroiliac joint steroid injection with 1 cc of 2% lidocaine and either 40mg Methylprednisolone (40mg/cc) vs 10mg dexamethasone (10mg/cc)

All injection for this protocol represent different variations all of which fall within the realm of standard of care.

Sacroiliac Joint Steroid injection:

- date of injection recorded
- side of injection (right or left)
- Needle as preferred by physician
- Oral anxiolysis with low dose benzodiazepine as determined by physician
- Local anesthetizing of skin as determined by physician not to exceed 2 cc of superficial 1% lidocaine
- Technique as determined by 2013 International Spine Intervention Society Practice Guidelines: patients will be prepped in sterile fashion with alcohol based antiseptic and sterile drapes. Patients will be positioned prone on the table. Access to the sacroiliac joint will be done. Using multiple fluoroscopic view including alternating lateral obliquity and cranio-caudal tilt, a spot 1-2 cm cephalad of the inferior posterior margin of the joint will be identified as the target. The needle will then be advanced in this view towards to target point until the sacrum is contact. The needle will then be withdrawn and slightly redirected into the joint space until loss of bony resistance is felt. Depth will then be confirmed via a spot lateral fluoroscopic view. Once needle position has been confirmed in both oblique and lateral view, minimal volume of contrast (0.2-0.5 cc of Omnipaque 300) will be administered through extension tubing under real-time fluoroscopy to ensure intra-articular placement and to rule out vascular flow pattern. Extension tubing will then be removed. The injectate of 1cc of 2% lidocaine and 1cc of either 10mg dexamethasone or 40 mg methylprednisolone will then be administered. The procedure can be abandoned at any time at the discretion of the physician or patient. Patients will be observed for 15 min post

- procedure in the procedure center recovery area and monitored for complications.
- Immediate relief of index pain will be documented prior to discharge

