### **Study Protocol**

Patients are divided into 2 groups based on randomization that occurs on the day of the first injection. Pre-procedural data categorization will be entered at the time of group assignment.

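### Patients are allocated before the contrast check that can stop the procedure, so abandonment after randomisation could differ by arm; the effect is small and cheap to prevent

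*Combined protocol and SAP*

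**What the plan says.** **Order of events.** Outcome Instruments (Injection Treatment) states: "On arrival to the procedure center eligible patients will be enrolled and consented. Patients will then be randomized to receiving sacroiliac joint steroid injection". The Study Protocol section agrees on the day: "Patients are divided into 2 groups based on randomization that occurs on the day of the first injection". The technique item then describes needle placement, followed by contrast, which "will be administered through extension tubing under real-time fluoroscopy to ensure intra-articular placement and to rule out vascular flow pattern". The steroid mixture is given after that.

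**Stopping.** The same technique item says "The procedure can be abandoned at any time at the discretion of the physician or patient". It gives no criterion, and it links abandonment neither to uptake nor to arm.

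**Why uptake matters.** Background and Significance gives a 5.3% incidence of vascular uptake and notes that it sometimes persists after several attempts to reposition. It continues: "In such cases, there is at least theoretical increased risk in administering particulate steroid and because of this the procedure may be cancelled". The next sentence reads: "An alternative to avoid this risk/complication or procedure termination would be administration of a non-particulate steroid".

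**Handling.** Study Timeline (Baseline) removes any patient without at least 80% relief when assessed within 15 minutes of injection. Analysis states intention to treat and bars crossover. The plan describes no operator blinding, no allocation concealment, and no status for a randomised patient who is never injected.

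**The concern.** The allocation is fixed before the one procedural finding that the plan's own rationale treats as mattering more for one steroid than for the other. An operator who knows the arm and meets persistent uptake has a documented reason to stop in a methylprednisolone patient and a documented reason to continue in a dexamethasone patient. Because crossover is barred, the steroid cannot be switched within protocol.

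The result could be a loss after randomisation that depends on the arm. The plan gives two incompatible answers on how to count such patients. Under the 80% relief rule they leave the study, since someone who was not injected cannot report relief after injection. Under intention to treat they stay, and uninjected patients may count as failures against one arm.

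**Working it through.** **Plan's own figure.** The plan gives no abandonment rate, so there is none to reproduce. The power calculation serves here only as a scale; whether 102 patients deliver the stated power is a separate question.

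**Inputs from the documents**
- Uptake u = 0.053 (Background and Significance). This is any uptake; the share that persists is not given.
- n = 51 per arm, response about 50%, target difference 20 points (Power Analysis).

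**Assumptions**
- A share f of uptake persists and ends in abandonment, with f from 0.2 to 1.
- All such abandonment falls in the methylprednisolone arm and none in the other. This is the extreme split.
- All 51 patients are counted at randomisation. If 51 means patients left after the 80% relief rule, the counts rise in proportion; the percentages stay the same.

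**Step 1: patients lost**, n × u × f
- f = 1: 51 × 0.053 = 2.70 patients, or 5.3% of the arm. Chance of at least one: 1 − 0.947^51 = 94%.
- f = 0.2: 2.70 × 0.2 = 0.54 patient, or 1.06% of the arm. Chance of at least one: 1 − 0.9894^51 = 42%.

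**Step 2: shift if kept as non-responders.** Write q = u × f for the fraction abandoned and r for the response rate they would have had. The arm's rate falls by q × r.
- f = 1, r = 0.5: 0.053 × 0.5 = 2.65 points, which is 2.65/20 = 13% of the target difference.
- f = 0.2, r = 0.5: 0.0106 × 0.5 = 0.53 point, which is 0.53/20 = 3% of the target.

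Setting r = 1, so that every abandoned patient would have responded, gives 5.3 points at f = 1. Nothing in the documents supports that value of r.

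**Step 3: shift if removed.** The retained rate is (0.5 − q × r)/(1 − q).
- r = 0.5: (0.5 − 0.5q)/(1 − q) = 0.5 for any q, so the shift is zero.
- f = 1: r = 0 gives 0.5/0.947 = 52.8% (+2.8 points); r = 1 gives 0.447/0.947 = 47.2% (−2.8 points).
- f = 0.2: r = 0 and r = 1 give about +0.5 and −0.5 point.

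Removal therefore distorts the comparison only if response in patients with persistent uptake differs from response in the rest, and the direction is unknown.

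**Step 4: precision.** Losing 3 patients from one arm multiplies the variance of the difference by (1/48 + 1/51)/(2/51) = 1.03, so the standard error rises by about 1.5%. This is negligible.

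**The case against.** The strongest reply is that the arm difference is inferred from background text. That section describes practice in general; it does not set a trial rule. The technique item applies the same contrast check to both arms, and read literally neither arm is injected until vascular flow is excluded. The discretion clause is generic and covers patients as well as physicians. The Background also says no catastrophic complication has been reported after sacroiliac injection with any steroid, which weakens the motive to stop. The documents do not say when the operator learns the allocation, so the gap may be one of reporting.

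Much of this stands. A reader might infer that operators will abandon more often in the methylprednisolone arm; the text supports only that they could. A reader might also infer that removing these patients biases the result in itself; step 3 shows that this needs a link between uptake and response, which the documents do not establish. Nor is 2.7 patients a forecast. It treats all uptake as persistent, whereas the Background confines persistence to some occasions after repeated attempts. The cited source's title also concerns lumbar spinal procedures, so the rate for the sacroiliac joint may differ.

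What does not fall away is the sequence. Stating the purpose of the contrast check does not say what follows when flow persists, and nothing in the plan keeps the operator unaware of the arm at that moment. Stating intention to treat does not settle the matter while the 80% relief rule removes the same patients.

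**Conclusion.** The point holds as a possibility created by the order of events. Randomisation precedes the contrast check, the Background supplies a reason to cancel that applies to one arm, and no blinding or neutral rule prevents that reason from acting. It does not show that abandonment will differ, or that the result will be biased.

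The size is small: between about 0.5 patient (20% persistence assumed) and a ceiling of 2.7 of 51 in one arm. The corresponding expected shift is about 0.5 to at most 2.7 points if these patients are kept as non-responders who would otherwise have responded at 50%. If they are removed, the expected shift is zero unless uptake is related to response. The case for acting is that the loss is avoidable at the design stage at almost no cost. It is a minor improvement and does not threaten the trial's conclusion.

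**What to change.** Keep eligibility and consent on arrival. State that the allocation is concealed and is opened only after the contrast check is complete and the operator has decided to proceed, immediately before the injectate is prepared. Then:

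- Patients abandoned before that point are not randomised. They are logged as such, with the reason.
- Patients abandoned after allocation stay in the intention-to-treat set, also with the reason recorded.

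This leaves the decision to abandon where the plan puts it and changes no dose or clinical rule. It ensures only that, at the first injection, needle placement, the reading of the contrast and the decision to proceed are all made without knowledge of the arm.

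The cost is a few sentences in the protocol, two log fields, and a short delay with the needle in place while the steroid is prepared. Patients in whom the operator stops leave the randomised population, but they would have had no injected outcome in any case.

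The change has two limits. A repeat injection uses the steroid first allocated (Follow-up; Repeat Injection Criteria), so the change does not blind that procedure. Nor does it resolve the wider conflict between the 80% relief removal rule under Baseline and intention to treat under Analysis, which must be reconciled separately.

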## Power Analysis

A total of 102 patients (51 dexamethasone and 51 methylprednisolone) will provide over 80% power to detect a difference of 20% between groups in the proportion of patients achieving at least moderate improvement on the NPRS using repeated measures binary logistic regression with a level of significance of  $\alpha = 0.05$ . This calculation is based on previous literature showing the proportion of patients achieving at least moderate improvement to be roughly 50% (1). Additionally, this calculation conservatively assumes moderate autocorrelation among the time points and includes an extra 15% to account for potential loss to follow up.

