### *Follow-up:*

Routine scheduled follow-up will occur at 4 weeks (+/- 1 week) and 3 months (+/- 2 weeks) at which times all follow-up measures will be obtained. All patients will follow-up with the primary investigator who performed the injection.

This study is intended to compare outcomes at 2-4 weeks and 3 months following an initial sacroiliac joint steroid injection. The patient's first injection will define the study start date and the outcome assessment timeline for that respective patient. During the 3 months from this start date, a participant may receive one additional injection per protocol, at which point the follow-up schedule will revert back to the beginning, starting with the 4 week time point and continuing up to the final 3-month follow-up. Repeat injection will be with the same steroid the patient initially randomized to. Only one additional injection is allowed within the protocol.

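### The stated power of over 80% with 102 patients does not follow from the Power Analysis inputs: on the natural reading it is at most 77–78%, and about 59–66% at a within-patient correlation of 0.5–0.3

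*Combined protocol and SAP*

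**What the plan says.** The Power Analysis section states: "A total of 102 patients (51 dexamethasone and 51 methylprednisolone) will provide over 80% power to detect a difference of 20% between groups". The outcome is at least moderate improvement on the NPRS, tested at alpha 0.05 "using repeated measures binary logistic regression". On the reference rate: "This calculation is based on previous literature showing the proportion of patients achieving at least moderate improvement to be roughly 50" per cent. On the remaining inputs: "this calculation conservatively assumes moderate autocorrelation among the time points and includes an extra 15% to account for potential loss to follow up".

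Three inputs are not given: a value for the correlation, whether the test is one- or two-sided, and how many time points enter the model. Other sections point to answers for the last two. The null in the Hypothesis section begins "There is no difference in percentage of patients with sacroiliac joint pain", which implies a two-sided test. The Follow-up section says "Routine scheduled follow-up will occur at 4 weeks (+/- 1 week) and 3 months (+/- 2 weeks"), which is two post-baseline visits, and the Analysis section uses the same two.

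**The concern.** For a treatment effect averaged over visits, positive correlation between a patient's visits reduces the information in the second visit. A sample size that allows for both moderate correlation and 15% loss should therefore be well above the size needed for two independent visits. It is not: 51 per arm is only slightly above the 47 evaluable per arm needed at zero correlation with no loss.

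This is the trial's only sample-size justification. The Background section says practitioners lack evidence on whether dexamethasone is as effective as particulate steroid, so a non-significant result is likely to be read as reassurance. A confidence interval would bear on that question more directly than power does. Still, a reader who trusts the stated power will believe the chance of missing a 20-point difference is below 20%.

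**Working it through.** **Inputs**

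- From the Power Analysis section: 51 per arm; 50% versus 70% (50% versus 30% gives the same power); alpha 0.05; 15% loss inside the 102.
- Inferred: two-sided (Hypothesis); two visits (Follow-up, Analysis). Response is improvement from baseline, so baseline cannot be a third response time point.
- Assumed: moderate correlation ρ means 0.3 to 0.5; ρ = 0 is shown as the best non-negative case.
- Evaluable per arm: 51 × 0.85 = 43.4, or 51 / 1.15 = 44.3, so 43–44.

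**Sample size for 80% power**

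One visit, pooled-variance formula, mean proportion 0.6:

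n = [1.960 × √(2 × 0.6 × 0.4) + 0.842 × √(0.5 × 0.5 + 0.7 × 0.3)]² / 0.2² = 93.0 per arm.

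For the mean of two visits, multiply by (1 + ρ)/2. This gives 46.5 (ρ = 0), 60.4 (ρ = 0.3) and 69.7 (ρ = 0.5) evaluable per arm. With 15% loss, the totals are 142–144 at ρ = 0.3 and 162–166 at ρ = 0.5. The lower figure multiplies by 1.15 and the higher divides by 0.85.

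**Power with the planned sample**

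The effective n per arm is m = 2n/(1 + ρ), and

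power = Φ{[0.2√m − 1.960 × √0.48] / √0.46}.

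Example, n = 44 and ρ = 0.3: m = 88/1.3 = 67.7; (1.646 − 1.358)/0.678 = 0.424; power 66.4%.

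| Evaluable per arm | ρ = 0 | ρ = 0.3 | ρ = 0.5 |
|---|---|---|---|
| 43 | 76.8% | 65.4% | 59.1% |
| 44 | 77.8% | 66.4% | 60.1% |
| 51 (no loss, outside the stated inputs) | 83.5% | 72.9% | 66.6% |

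A simulation of correlated binary visits with a robust Wald test on the logit scale (20,000 runs per case) agrees: 76.3 / 65.0 / 58.5% with 43 per arm and 77.5 / 66.4 / 59.8% with 44. To reach 80% with 43–44 per arm, ρ would have to be negative (−0.075 to −0.054).

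**Sensitivity**

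- Reference rate 45–55%, 43–44 per arm: 76–80% / 64–69% / 58–63% at ρ = 0 / 0.3 / 0.5.
- All loss after the 4-week visit (51, then 43 per arm): m = 2 × 43/(1 + ρ) + 8 = 94.0 / 74.2 / 65.3, giving 80.4 / 70.4 / 64.9%.

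**Attempts to reproduce the stated figure**

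- One-sided, two visits, ρ = 0.2: n = 43.9, rounded up to 44; 44 × 1.15 = 50.6, rounded up to 51 per arm, total 102. Power with 44 per arm is 80.1%.
- Two-sided, three time points (exchangeable correlation), ρ = 0.2: n = 43.4, rounded up to 44, and again 102. Power with 44 per arm is 80.5%.
- The same readings at ρ = 0.3 with 44 per arm: 77.2% one-sided; 75.1% with three exchangeable time points, or 78.9% with autoregressive correlation.
- One-sided with no loss: 82.4% at ρ = 0.3, and 80% up to ρ of about 0.40.
- One-sided and three time points together, 43–44 per arm: 80% up to ρ of about 0.4 (exchangeable) or 0.5 (autoregressive).

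Either of the first two could be the source of 102.

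**Detectable difference with 80% power, 43–44 per arm**

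Two visits: 23–25 points at ρ = 0.3–0.5.

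**Separate point: the 2–4 week outcome alone**

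The Primary Outcomes section names only this time point as primary. With m = n, power is 47.3% (43 per arm) or 48.2% (44 per arm), and the detectable difference is 28–29 points. The Power Analysis section makes no claim about this comparison.

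**The case against.** The strongest reply is that the section is under-specified rather than miscalculated. Two settings return exactly 102, so the original calculation may be internally correct with unreported inputs. That stands as an account of how the number may have arisen. It does not rescue the claim, because those inputs conflict with the no-difference null or the two-visit schedule. The restart after a repeat injection ("at which point the follow-up schedule will revert back to the beginning") can give some patients extra visits, but nothing in the Power Analysis section says these were counted.

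Second, the large shortfall rests on an assumed correlation of 0.3–0.5. This is fair: the direction is secure but the size is not. Without that assumption the gap is only 2–3 points, and late loss or a reference rate at the edge of 45–55% closes it to about 80%. Both of those routes need zero correlation, which contradicts the stated moderate autocorrelation.

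Third, the low power at 2–4 weeks alone is a different issue and does not show this calculation to be wrong. I agree, and it carries no weight in the conclusion.

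**Conclusion.** The concern holds. With a two-sided test, two visits and 43–44 evaluable per arm, power for 50% versus 70% is 77–78% at zero correlation and falls with any positive correlation. At ρ = 0.3–0.5 it is about 66% down to 59%, a type II error of about 34–41%.

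The result rests on two inferences from other sections (two-sided, two visits) and on one assumption (the correlation range). Even if all 51 per arm were evaluable, 80% would require ρ below about 0.10. The stated power needs correcting before the plan is relied on.

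**What to change.** Keep N = 102 and rewrite the Power Analysis section:

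- State the correlation, sidedness, number of time points and evaluable number per arm. Say whether 102 counts patients before or after the post-injection relief check described under Baseline in the Study Timeline.
- Decide whether the primary analysis is the 2–4 week comparison (Primary Outcomes) or the two-visit model (Hypothesis, Power Analysis, Analysis).
- Replace the power figure with one recalculated by the sponsor for that analysis after 15% loss, using its own correlation. As a guide, expect about 59–66% for two visits if ρ is 0.5–0.3, or about 47–48% at 2–4 weeks alone.
- Add the difference detectable with 80% power: about 23–25 points for two visits on the same correlations, or 28–29 points at 2–4 weeks alone.
- If the original calculation was one-sided or used three time points, say so and reconcile it with the Hypothesis and Follow-up sections.

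The cost is a text change and one decision on the primary time point or points. No extra patients are needed. The stated power becomes less favourable and the detectable difference larger.
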